12.1.8. Follow-Up of AEs and SAEs

All AEs must be followed during the course of the study until the AE resolves, is no longer of clinical concern, has stabilized or is otherwise explained, or the subject is lost to follow up.

AEs ongoing at the final visit that are deemed to be “possibly, probably, or definitely” related or of other clinical significance must be followed for as long as necessary to adequately evaluate the safety of the subject or until the event stabilizes, resolves, or is no longer of clinical concern. If resolved, a resolution date for the AE should be documented on the CRF. The Investigator must ensure that follow up includes any supplemental investigations indicated to elucidate the nature and/or causality of the AE. This may include additional laboratory tests or investigations, or consultation with other healthcare professionals, as considered clinically appropriate by the Investigator.

All subjects showing possible drug-induced liver injury should be followed until all abnormalities return to normal or to the baseline state. Drug-induced liver injury may develop or progress even after the causative drug has been stopped. Results should be recorded in the CRF. Note that longer follow-up can sometimes reveal an off-drug repetition of what had appeared to be drug-induced liver injury, indicating that liver injury was related to underlying liver disease.

12.1.9. Pregnancy and Follow up

Pregnancies are not considered AEs in and of themselves; however, if a female study participant becomes pregnant while she is enrolled in the clinical study, she must interrupt treatment with investigational product immediately (see [Section 8.4.2.1](#)) and the Sponsor must be notified within 24 hours of the Investigator’s awareness of the pregnancy by completing the Pregnancy CRF in the EDC system and downloading and completing the Pregnancy Report Form. The Pregnancy Report Form must be emailed to [contact] or faxed to [contact]. The subject and neonate must be followed for outcome information and/or as considered appropriate by the Investigator and Sponsor.

The subject may restart investigational product when she is no longer pregnant or breastfeeding (if applicable) at the discretion of the Investigator and after discussion with the Medical Monitor. The subject must have a negative pregnancy test before restarting investigational product. If a subject’s pregnancy is terminated early (planned or unplanned), she must have termination of the pregnancy confirmed by a serum β -hCG test before restarting investigational product.

Completing the Pregnancy Report Form is not a substitute for reporting an AE/SAE when and AE/SAE has occurred. In the situation when an AE/SAE has occurred, the AE/SAE reporting procedures described in [Section 12.1.4](#) must also be followed.

12.2. Other Safety Parameters

12.2.1. Medical History/Demographics

A complete medical history and PBC disease-specific history will be obtained from the subject at Screening. Smoking and alcohol consumption history and current habits will be recorded. Demographic characteristics (age, gender, race, and ethnicity) will be recorded.

12.2.2. Physical Examination

To assess for clinical findings, the Investigator or designee will perform a physical examination at the timepoints specified in the Schedule of Study Procedures ([Section 7.1.2](#)). A basic physical examination should be performed, including all body systems pertinent to the subject. Any clinically significant abnormality should be reported on the AE CRF page for findings that appear after consent, and on the medical history CRF for any finding present prior to consent. Information about smoking and alcohol consumption habits will be collected at the same (follow-up) timepoints as the physical exam.

12.2.3. Vital Signs

Vital signs will be assessed at indicated visits: height, weight, temperature, sitting heart rate, respiratory rate, and sitting blood pressure. When taking heart rate, respiratory rate, and blood pressure readings, subjects should be seated quietly for a minimum of 3 minutes before the readings are taken.

12.2.4. Electrocardiogram

Standard 12-lead ECGs will be collected at the Screening Visit 1, Month 12, and at EOT/EOS. The Investigator or designee will review the 12-lead ECG and findings will be recorded in the CRF as normal, abnormal but not clinically significant, or abnormal and clinically significant. Any clinically significant abnormality on ECGs should be reported on the AE CRF page.

Investigative sites must retain a copy of all 12-lead ECGs evaluated by the Investigator or designee. These ECGs must be clearly labeled with the subject's initials, Subject ID number, date, and time.

12.2.5. Dual Emission X-Ray Absorptiometry

A bone density assessment will be done using the DEXA scan.

12.2.6. Subject Questionnaires

Information about the subject's PBC disease history (ie, date of diagnosis, treatment history, pruritus history, signs and symptoms, and including smoking history) will be collected during Screening. At subsequent study visits (see [Section 7.1.2](#)), subjects will be asked to complete the following questionnaires; they may be asked to initial and date to document confirmation of their

responses, and the questionnaires should be filed in the subject's study records. These may require transcription to the CRF by study site staff.

- 5-D Pruritus Questionnaire: This is a questionnaire that has been validated in several different diseases. It assesses symptoms in terms of 5 domains: degree, duration, direction, disability and distribution ([Elman 2010](#)).
- Pruritus VAS: A Visual Analogue Scale (VAS) will also be used to assess pruritus in individual subjects.

12.2.7. Laboratory Assessments

Subjects will be instructed to attend each of their study visits (except Screening) in a fasted state, and subjects should remain fasted until their blood samples have been collected. At each visit, the Investigator or designee will verify that the subject has fasted for at least 8 hours and record fasting status in the source and CRF. If the subject reports having eaten (water is permitted) within 8 hours, the Investigator or designee will document accordingly in the source and CRF and remind the subject that fasting is required prior to all study visits.

Blood samples for serum chemistry and hematology will be collected at every visit as detailed in the Schedule of Study Procedures ([Section 7.1.2](#)). The number and volume of samples to be collected at each visit will be detailed in the laboratory manual.

Full instructions concerning the number and type of samples to be collected at each visit, the required sample volumes, sample collection methods, sample processing, labeling, and shipping will be provided by the central clinical laboratory in a study specific laboratory manual. All necessary collection supplies will be provided by the central laboratory and will be appropriately assembled for the specific evaluations required at each visit.

All subjects with laboratory tests containing clinically significant abnormal values are to be followed regularly until the values return to normal ranges; until a valid reason, other than investigational product-related AE, is identified; or until further follow up is deemed medically unnecessary.

Laboratory samples will be stored for a maximum of up to 1 year after the end of the study (depending on stability) in the event that retesting is required, and destroyed after 1 year if not analyzed.

The list of laboratory analytes to be tested is shown in [Table 10](#).

Table 10: List of Laboratory Analytes to be Tested

Laboratory Assessment	Analyte
Serum Chemistry	Albumin, blood urea nitrogen (BUN), creatinine, direct bilirubin, total bilirubin, aspartate aminotransferase [AST, SGOT], alanine aminotransferase [ALT, SGPT], ALP, GGT, electrolytes [calcium, chloride, potassium, sodium], glucose, total protein, and blood lipids (total cholesterol, LDL, HDL and very low density lipoprotein [VLDL] fractions and triglycerides [TG]), magnesium, phosphorus, bicarbonate, unconjugated (indirect) bilirubin, conjugated (direct) bilirubin, free fatty acids
Hematology	Hemoglobin, hematocrit, white blood count with differential, neutrophils, lymphocytes, monocytes, eosinophils, basophils, platelets, red blood cell count (including MCV, MCH, MCHC)
Coagulation	Prothrombin time (PT), partial thromboplastin time (PTT), international normalized ratio (INR)
Urinalysis	pH, specific gravity, total protein, glucose, ketones, bilirubin, blood, microscopic exam, urobilinogen, albumin, creatine, leucocytes, nitrates, albumin/creatinine ratio (if positive)
Biomarkers of Hepatic Fibrosis and/or Inflammation	IgM, C-reactive protein (CRP), TNF- α , FGF-19, CK-18, ELF, and others as determined during course of study
Genetics	DNA including single-nucleotide polymorphisms (SNPs) that may be involved in PBC; RNA
Blood Sample for Future Analysis	PBC autoantibodies and other cytokines and interleukins TBD
Other	OCA (parent and conjugates [glyco and tauro], OCA-glucuronide) and C4

The Investigator should manage subjects with clinically significant lipoprotein abnormalities using local standard of care procedures as appropriate after assessing the individual subject's total cardiovascular risk profile.

Urine-based β -hCG pregnancy tests will be performed in female subjects of childbearing potential per protocol specified visits. If a urine pregnancy test is positive, a serum pregnancy test must be performed to confirm the result. If positive, the Sponsor must be notified and the subject will be followed, as outlined in [Section 12.1.9](#) through pregnancy outcome.

MELD scores, Child-Pugh score, and MRS will be calculated at screening, and at quarterly (MELD and Child-Pugh scores) or semi-annual (MRS) visits based on serum chemistry and coagulation.

13. STATISTICAL METHODS

A statistical analysis plan (SAP), providing details about the specific planned analyses and hypothesis tests, will be prepared and approved by the Sponsor and its designees prior to study database lock, propensity score determination, and unblinding of the double-blind subject treatment assignments.

13.1. Efficacy Analysis

13.1.1. Analysis Populations

The following subject populations will be evaluated and used for presentation and analysis of the data:

- The Intent-to-Treat (ITT) Population will include all randomized subjects who receive any amount of investigational product (OCA or placebo). The ITT Population will be the primary population used for efficacy analyses. Treatment assignment will be based on the randomized treatment.
- The Safety Population will include all subjects who received any amount of investigational product (placebo or OCA). The Safety Population will be the primary population used for safety analyses. Treatment assignment will be based on the treatment actually received.
- The PK population will include all OCA subjects who have at least one confirmed fasted analyzable sample. Subjects must have been fasting for approximately 8 hours prior to the visit and must not have any major protocol deviations that potentially affect exposure levels. The PK population will be used for OCA PK analyses.
- The Overall Historical Control Population will include subjects from the United Kingdom (UK) -PBC Group and Global PBC Study Group databases with demonstrated comparability to randomized subjects in this clinical study (747-302) with respect to both subject characteristics and disease progression.
- The UK-PBC Historical Control Population will include subjects from the UK-PBC Group databases with demonstrated comparability to randomized subjects in this clinical study (747-302) with respect to both subject characteristics and disease progression.
- The Global PBC Historical Control Population will include subjects from the Global PBC Study Group database with demonstrated comparability to randomized subjects in this clinical study (747-302) with respect to both subject characteristics and disease progression.

13.1.1.1. Comparability of Historical Controls

Utilization of both historical control/observational databases (UK-PBC and Global PBC Study Group), with more than 6000 subjects each, allow for a rigorous subject level meta-analysis. The historical databases include long-term follow up, detailed subject-level information such as baseline clinical characteristics, longitudinal liver biochemistry, and long-term outcomes, and

span a broad range of subject characteristics that may influence disease (disease state, age, gender, and regional differences in standard of care). Historical controls from both databases will be chosen based on the same study inclusion/exclusion criteria where possible.

13.1.2. Determination of Sample Size

The following assumptions were used in sample size calculations:

- Exponential survival curves, placebo survival estimate of 0.6 at 8 years with a hazard ratio of 0.60, and total study duration of 10 years (from first subject enrolled), allowing for 4 years subject accrual and 6 years of follow up.
- Subjects will be randomized in a 1:1 ratio to placebo or OCA.
- The 2 groups will be compared using a 2-sided log rank test at the 5% level of significance.
- Two interim analyses and one final analysis are planned.

Based on the randomization ratio, significance level, and assumed hazard ratio, a total of 127 events (both groups combined) will provide 80% power to demonstrate a statistically significant difference between OCA and placebo on time to liver-related outcomes, including all-cause mortality.

In addition, based on the remaining assumptions stated above, it is estimated that approximately 428 subjects will be enrolled to attain 127 events.

13.1.2.1. Sample Size Monitoring

Conducting a long-term outcomes study given the low disease prevalence, relatively slow disease progression, and ethical considerations, which in combination will impact recruitment and event rates, is inherently difficult. As stated in ICH E9, in long-term trials there is an opportunity to check the assumptions that underlay the original design and sample size calculations. The power stated above depends on the total number of events. Thus, the overall survival function can be estimated without unblinding.

Therefore, the aggregate event rate and sample size based on recruitment and retention will be evaluated in a blinded manner quarterly. This evaluation will determine if any increases in number of subjects are required in order to obtain a total of 127 adjudicated events for the final analysis in the combined groups. Specifically, the pooled number of events will be available during the study in a blinded manner, without any knowledge of the comparative efficacy in the treatment groups. This method for evaluating the sample size does not inflate the type I error rate. Additional subjects may be enrolled as appropriate.

13.1.3. Primary Efficacy Analysis

The primary efficacy endpoint will be the time to first occurrence of one of the following post-randomization:

- Death (all-cause)
- Liver transplant

- MELD score ≥ 15
- Hospitalization (as defined by a stay of 24 hours or greater) for new onset or recurrence of:
 - Variceal bleed
 - Hepatic encephalopathy (as defined by a West Haven score of ≥ 2)
 - Spontaneous bacterial peritonitis (confirmed by diagnostic paracentesis)
- Uncontrolled ascites (diuretic resistant ascites requiring therapeutic paracentesis at a frequency of at least twice in a month).
- Hepatocellular carcinoma confirmed by 2 complimentary imaging modalities unless confirmed by biopsy

The primary efficacy analysis will compare randomized OCA to randomized placebo with respect to the primary efficacy endpoint using the ITT population. Only adjudicated events will be included in analyses. The 2 treatment groups will be compared using the log rank test stratified by the randomization stratification factor. Kaplan-Meier (KM) estimates of the distribution of the time-to-event will be tabulated and graphed by treatment group. The tabulation will include the KM estimate of the medians and corresponding 95% confidence intervals (CIs), if the medians can be estimated. The number and percent of subjects censored and with events will be presented. The hazard ratio and 95% CI will be determined based on a Cox regression model stratified by randomization strata to estimate the magnitude of the effect.

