7. INVESTIGATIONAL PLAN

7.1. Overall Study Design

This is a Phase 4, double-blind, randomized, placebo-controlled, multicenter study. Eligible subjects will have a diagnosis of PBC with bilirubin levels of $>ULN$ and $\leq 5 \times ULN$ and/or ALP $>3 \times ULN$. Subjects enrolled will be at higher risk of liver-related clinical complications.

Approximately 428 subjects meeting all enrollment criteria will be recruited into the study over an approximate 4-year period, randomly allocated to treatment with either OCA or matching placebo in a 1:1 ratio (Figure 1). Subjects will be screened during a 1 to 8-week Screening period prior to entering the study to allow for the collection of repeat serum chemistry samples (at least 2 weeks apart) to confirm pretreatment ALP and total bilirubin values (refer to Section 9.7.6). Randomization will be stratified by UDCA treatment (yes/no) and baseline bilirubin categories ($>ULN/\leq ULN$). In addition to the placebo control arm, multiple historical control groups (concurrent and retrospective) will be used.

Subjects will be dosed according to their cirrhosis status and Child-Pugh Score. Subjects who are non-cirrhotic or classified as Child-Pugh A at Screening will initiate investigational product once daily with 5-mg OCA or matching placebo. Following 3 months of once daily treatment with investigational product, the dose should be titrated to a maximum 10 mg OCA or matching placebo once daily, based on tolerability and biochemical response (see Section 7.3).

[figure not shown]
Subjects with cirrhosis (see Section 9.7.3) and classified as Child-Pugh Class B or Child-Pugh Class C will follow a modified dosing regimen, and will initiate investigational product once weekly with the 5-mg OCA or matching placebo dose. In addition, these subjects will follow a modified titration plan, which is outlined in Appendix A.

It is anticipated that subjects will be followed for a minimum of approximately 6 years. The study will continue until approximately 127 adjudicated primary endpoint events have been accrued in unique subjects, or until the Sponsor (eg, based on advisement by the Data Monitoring Committee; DMC) terminates the study.

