8.3. Subject Exclusion Criteria

1. History or presence of other concomitant liver diseases including:
 - Hepatitis C virus infection
 - Active hepatitis B infection; however, subjects who have seroconverted (hepatitis B surface antigen and hepatitis B e antigen negative) may be included in this study after consultation with the Medical Monitor.
 - Primary sclerosing cholangitis
 - Alcoholic liver disease
 - Definite autoimmune liver disease or overlap hepatitis
 - Nonalcoholic steatohepatitis
 - Gilbert's Syndrome
2. Presence of clinical complications of PBC or clinically significant hepatic decompensation, including:
 - History of liver transplant, current placement on a liver transplant list, or current MELD score >12 . Subjects who are placed on a transplant list despite a relatively early disease stage (for example per regional guidelines) may be eligible as long as they do not meet any of the other exclusion criteria.

- Cirrhosis with complications, including history (within the past 12 months) or presence of:
 - Variceal bleed
 - Uncontrolled ascites
 - Encephalopathy
 - Spontaneous bacterial peritonitis
 - Known or suspected hepatocellular carcinoma
 - Prior transjugular intrahepatic portosystemic shunt procedure
 - Hepatorenal syndrome (type I or II) or Screening (visit 1 or 2) serum creatinine >2 mg/dL (178 µmol/L)
3. Mean total bilirubin >5× ULN
 4. Subjects who have undergone gastric bypass procedures (gastric lap band is acceptable) or ileal resection or plan to undergo either of these procedures.
 5. Other medical conditions that may diminish life expectancy, including known cancers (except carcinomas *in situ* or other stable, relatively benign conditions such as chronic lymphatic leukemia).
 6. If female: plans to become pregnant, known pregnancy or a positive urine pregnancy test (confirmed by a positive serum pregnancy test by the central laboratory), or lactating.
 7. Known history of human immunodeficiency virus infection.
 8. Medical conditions that may cause non-hepatic increases in ALP (eg, Paget's disease or fractures within 3 months).
 9. Other clinically significant medical conditions that are not well controlled or for which medication needs are anticipated to change during the study.
 10. History of alcohol abuse or other substance abuse within 1 year prior to Day 0.

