9.4. Randomization and Blinding

This study will be conducted in a double-blind, placebo-controlled manner. Allocation to one of two treatment groups (OCA or placebo) will occur on a 1:1 ratio across sites and will be stratified by UDCA treatment (yes/no) and mean baseline bilirubin categories ($>ULN/\leq ULN$), as specified by the central laboratory. The randomization will be based on a predefined randomization code (generated by the Sponsor or designee) using an interactive web response system (IWRS), which the Sponsor intends will serve as a computer-based subject registration system at Screening and Day 0. The IWRS will serve as an investigational product inventory and management system and may be integrated with the study database.

The Investigator or designee will be required to register the subject in the IWRS and may be prompted to provide subject data necessary to properly randomize and allocate the subject to treatment. A randomization number will be assigned (refer to [Section 9.5.2](#) below) and investigational product dispensing information (ie, bottle number[s]) will be provided.

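### The primary log-rank test is valid and adequately powered as planned, but leaves out screening MELD and the measured baseline bilirubin, so it forgoes power that data already collected could supply

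*Protocol*

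**What the plan says.** Section 13.1.3 names the primary test: "The 2 treatment groups will be compared using the log rank test stratified by the randomization stratification factor". The Version 4 synopsis repeats it unchanged. The effect estimate follows the same structure: "The hazard ratio and 95% CI will be determined based on a Cox regression model stratified by randomization strata". No baseline covariate is named in either. Section 13.1.4 carries the method over to the time-to-event key secondaries, and time to MELD ≥15 is tested first among these (section 13.1.10).

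Section 9.4 has allocation "stratified by UDCA treatment (yes/no) and mean baseline bilirubin categories", split at ULN. That makes two binary factors and four strata.

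Two more detailed severity measures are available before randomization:

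- **MELD.** Section 12.2.7: "MELD scores, Child-Pugh score, and MRS will be calculated at screening, and at quarterly" visits thereafter. Section 8.3 excludes "History of liver transplant, current placement on a liver transplant list, or current MELD score >12", and MELD ≥15 is itself a primary event.
- **Total bilirubin.** At least two screening values are averaged to determine eligibility (section 9.7.6), and eligible values run up to 5× ULN (section 8.2).

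Section 13.1.2 sizes the trial on the log-rank test ("The 2 groups will be compared using a 2-sided log rank test at the 5% level of significance") and states that "a total of 127 events (both groups combined) will provide 80% power".

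**The concern.** One component of the composite is a threshold on a score that every subject already has at entry. A subject at the entry cap of MELD 12 is 3 points from an event; a subject entering lower is further away. The primary test sees none of this. The stratum above ULN pools subjects from just over ULN to 5× ULN. The stratum at or below ULN carries no further severity information, and under the Version 4 synopsis, which requires only 30% of subjects above ULN, it could hold up to 70% of the trial.

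The sponsor recognises that such values matter. The rationale for Version 3.1 (Appendix G) describes ALP and bilirubin as having proven prognostic utility, and says the entry limits were widened to bring in both earlier and more advanced disease. The ANCOVA in section 13.1.4 already uses baseline values as covariates.

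What is at stake is efficiency. The trial is expected to take about 10 years to reach 127 events in a rare, slowly progressing disease. Power recovered from baseline data needs no further subjects, visits or events.

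**Working it through.** **1. Reproduce the plan's figures.** Inputs from section 13.1.2: HR 0.60, two-sided 5%, 1:1, 127 events, placebo event-free proportion 0.6 at 8 years, 4 years' accrual plus 6 years' follow-up. The 10% dropout is from the Version 4 synopsis; the looks at 50% and 75% are from section 13.1.12.

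- Schoenfeld: 4(1.960 + 0.842)² / (ln 0.60)² = 4 × 7.849 / 0.2609 = 120.3, so 121 events. Power at 127: Φ(√127 × 0.5108/2 − 1.960) = Φ(0.918) = 82.1%.
- Freedman: (1.6/0.4)² × 7.849 = 125.6, so 126 events. Power at 127: Φ(√127 × 0.25 − 1.960) = 80.4%.
- With Lan-DeMets O'Brien-Fleming looks at 64, 96 and 127 events (critical values 2.95, 2.35, 2.02), power is 81.3% (Schoenfeld) or 79.7% (Freedman).
- Sample size: the placebo hazard is −ln(0.6)/8 = 0.0639 per year. The event probability averaged over arms is 0.331; 127/0.331 = 384, and 384/0.9 = 427, against 428 stated.

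The plan's 127 events, 80% power and 428 subjects all reproduce.

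**2. Effect of adjustment: stratified Cox test.** Simulation of 428 subjects in four strata, uniform 4-year accrual, analysis at the 127th event. One normal within-stratum score stands for MELD and log bilirubin jointly. Critical value 1.96, 3,000 to 4,000 runs per row. Assumptions not in the documents: the score's strength, half the subjects above ULN, log-HR 0.8 between bilirubin strata, 95% on UDCA, and a base hazard of 0.03 per year in the lower bilirubin stratum.

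| HR per SD of score | 0.60 is the HR the log-rank sees: unadjusted → adjusted | 0.60 is the covariate-conditional HR: unadjusted → adjusted |
|---|---|---|
| 1.35 | 81.5% → 82.3% (+1) | 80.8% → 82.0% (+1) |
| 1.65 | 83.5% → 86.4% (+3) | 77.7% → 80.8% (+3) |
| 2.0 | 82.4% → 89.0% (+7) | 73.8% → 80.7% (+7) |
| 2.5 | 83.6% → 92.5% (+9) | 68.0% → 80.0% (+12) |

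The Monte Carlo standard error of each power figure is about 0.6 to 0.7 points (√(0.8 × 0.2/4000) = 0.6). With no treatment effect, one-sided rejection in favour of OCA was 2.2% (log-rank) and 2.0% (adjusted Cox) against a nominal 2.5%.

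**3. Effect of adjustment: stratified log-rank test.** A second simulation, with 5,000 runs per setting, adjusted the log-rank score by linear augmentation. It held the marginal HR at 0.60 and placebo survival at 0.60 at 8 years, and assumed two equal strata with a log-HR of 1.0 between them.

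| Within-stratum SD of log-hazard (HR per SD) | Unadjusted → adjusted log-rank |
|---|---|
| 0.5 (1.65) | 81% → 84% (+3) |
| 0.75 (2.12) | 82% → 87% (+5) |
| 1.0 (2.72) | 81% → 89% (+8) |

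Type I error was 4.7% to 5.0%. An adjusted Cox test in the same settings gave 83%, 89% and 92%.

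**4. In events.** By the Schoenfeld formula at HR 0.60, an unadjusted test needs about 134, 146 and 156 events for 84%, 87% and 89% power: 7, 19 and 29 more than 127.

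**Not computed.** Both simulations ignore the interim looks, and neither addresses time to MELD ≥15, for which the documents give no event count.

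**The case against.** The strongest reply is that nothing here is wrong. A log-rank test stratified by the randomization factors is valid, it is the test the sample size was built on, and it delivers the stated power. This stands in full. A reader might infer that the trial is underpowered or the test faulty; the documents do not support that. Power falls below 80% only if 0.60 is read as a covariate-conditional hazard ratio. Section 13.1.2 does not say so, and it pairs 0.60 with the log-rank test.

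The size is also open to challenge. A reader might take 3 to 8 points as an established loss, or apply a generic covariate-outcome correlation such as 0.5 and claim more. No section gives a prognostic strength or a correlation, and a weak covariate gains only about 1 point. One bilirubin split is already in the strata, so only within-stratum information counts.

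A reader might also infer a quantified power loss for time to MELD ≥15. The same direction is plausible there, but no figure is available.

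Finally, the change is not free. Section 13.1.8 says the planned primary analysis would not be revised without regulatory agreement. The sentence follows a DMC-driven scenario, but replacing the primary test is the same kind of change. The SAP may add adjusted supportive analyses, and the body of Version 4 section 13.1.3 is not shown. Neither point alters the primary test, which the Version 4 synopsis restates.

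**Conclusion.** The point holds as forgone efficiency, not as an error. The protocol fixes a primary test that uses two binary factors and omits two collected baseline measures closely tied to the endpoint. Adjusting for them raises power at the same 127 events, with type I error controlled in both simulations.

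The gain depends on an assumed joint within-stratum strength of MELD and log bilirubin: about 1 point at an HR per SD of 1.35, 3 at 1.65, 5 to 7 at 2.0 to 2.1, and 9 to 12 at 2.5. The 5 is the adjusted log-rank at 2.1; the other figures are for the adjusted Cox test. For the adjusted log-rank the gain is about 3 to 8 points over a log-hazard SD of 0.5 to 1.0. If 0.60 is the marginal hazard ratio, all of this is added to a planned 80% that is already met.

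**What to change.** Before the first interim look, and with regulatory agreement:

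- In section 13.1.3, and through section 13.1.4 for time to MELD ≥15, prespecify a covariate-adjusted stratified log-rank test. Keep the randomization strata and add screening MELD and log baseline total bilirubin. The null hypothesis is unchanged.
- Use the same statistic at both interim looks and the final analysis.
- Report the unadjusted stratified log-rank test as a sensitivity analysis, and a stratified Cox hazard ratio adjusted for the same covariates, labelled as conditional.
- If the primary test is not to be changed, at minimum prespecify the adjusted analysis as supportive.

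The cost is protocol and SAP wording, some programming, one more estimate to explain (the conditional hazard ratio differs from the unadjusted one), and agreement with regulators on the change of primary test. No new data are needed.
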